14.3 Treatment re-initiation

Patients who discontinue copanlisib may restart if they meet requirements set out in Section 9.9 and after discussion with study PI. Patients who have a complete response, then restart copanlisib for progression will be counted as a progression. Future responses will be censored.

14.4 Exploratory assessments

Baseline targeted sequencing of patient tumor samples will be analyzed by Fisher's exact test for correlation with response/resistance and log rank test for correlation with duration of response. The proportion of patients with detectable ctDNA will be estimated along with a 95% CI as well as a mean (variance) of ctDNA. I plan to plot the variant allele frequency of each mutation over time for each patient. ctDNA levels will be correlated with response or duration of response to treatment. A multivariate logistic regression model will be fit with best response to treatment as the outcome variable and ctDNA and patient-related factors as covariates. To test the relation between ctDNA and disease status, defined as no evidence of radiographic disease (CR) vs radiographic disease (combined PR, SD, POD), all serial measurements will be used in a logit model with generalized estimating equations to correct for within-patient correlations. Logistic regression will be used to assess the correlations between the markers and tumor status. Overall survival (OS) and progression-free survival (PFS) will be assessed by Kaplan-Meier methods. The effect of ctDNA on OS will be analyzed as a time-dependent covariate using a Cox proportional hazards model. Similar evaluations will be performed on ctRNA. The statistical analysis will be primarily descriptive and the data will provide initial information regarding the kinetics of response and sensitivity of the assay itself.

Pharmacokinetic assessments will be based on patients in the phase I dose escalation level 1 and 2 cohorts. A non-compartmental analysis (NCA) will be performed in this study and pharmacokinetic parameters will be calculated using WinNonlin, in the latest version. Based on the plasma concentration–time data, the following pharmacokinetic parameters will be calculated.

	Copanlisib	Ibrutinib
Main PK parameters	Cycle 1 Day 15 Cmax, AUC(0–24)	Cycle 1 Day 15 Cmax, AUC(0–tlast), AUC(0–24) and AUC
Additional PK parameters	M-1, if applicable Cmax, AUC(0–tlast)	tmax, tlast, t1/2 CL and Vd if possible

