9.0 TREATMENT/INTERVENTION PLAN

9.1. Study Treatment

The investigational agents to be used in this study are copanlisib and ibrutinib. Copanlisib is given intravenously on days 1, 8, and 15 of 28 day cycles. Ibrutinib is given orally every day on 28 days cycles. The maximum duration of treatment is 36 cycles not exceeding 36 months. Dose changes or interruptions are allowed per below guidelines and must be recorded appropriately.

Study personnel will maintain a log of all drugs supplied to the patient. Drug supplies for each patient will be inventoried and accounted for. Subjects will be given diary cards to complete for the ibrutinib taken at home. Subjects must bring the diary cards to the site on every visit so study site personnel can verify compliance.

9.1.1 Copanlisib administration:

Copanlisib is supplied as lyophilized preparation in a 6-mL injection vial. The total amount of copanlisib, BAY 80-6946, per vial is 60 mg. The solution for IV infusion is obtained after reconstitution of the lyophilisate with 0.9% sodium chloride solution. Please refer to the Pharmacy Instructions for detailed instructions for the reconstitution of the lyophilisate and for further dilution of the reconstituted solution. Study drug is administered in a normal saline solution, intravenously, over 1 h (or per MSK protocol). No intravenous glucose preparations should be administered on the days of infusion. Dosing is weekly for the first 3 weeks of a 28-day cycle (on Days 1, 8, and 15), followed by a 1-week break (i.e., no infusion on Day 22). Patients will be on 30 mg, 45 mg or 60 mg depending on their dose level.

Laboratory blood tests on day 1 of copanlisib treatment must follow the below criteria:

Table 9-1: Laboratory test criteria for Day 1 dose of subsequent cycles

Laboratory Test	Criteria for Day 1 dose (Cycle 2 and higher)
Glucose	< 160 mg/dL (fasting) or < 200 mg/dL (non-fasting)
Hemoglobin	$\geq 8 \text{ g/dL}$ ^a
ANC	$\geq 1 \times 10^9$
Platelets	$\geq 75 \times 10^9$ ^b

ANC = Absolute neutrophil count;

a: If hemoglobin is < 8 g/dL but $\geq 6 \text{ g/dL}$ on the day of planned study drug administration it is permissible to give the study drug dose as scheduled and transfuse within 48 hours after the dose, if the patient is hemodynamically stable and in opinion of investigator benefits outweigh risks. Rationale and treatment should be recorded in source document and eCRF.

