Ibrutinib will be administered once daily continuously until disease progression, intolerance, or completion of 36 cycles, not exceeding 36 cycles since start of therapy whichever comes first. Patients will be instructed to take 420 mg or 560 mg depending on the treating cohort.

Ibrutinib should be administered at about the same time each day orally with 8 ounces or approximately 240 mL of water. The drug should be swallowed intact and subjects should not attempt to crush dissolve the tablets in water. If a dose is missed, the dose may be taken as soon as possible on the same day with a return to the normal schedule the following day. Extra tablets of ibrutinib should not be taken to make up for the missed dose. If a patient vomits the dose, the dose should not be retaken. On days when patients are receiving copanlisib and ibrutinib, patients should take their dose of ibrutinib in clinic just prior to the copanlisib infusion.

9.2. Definitions of dose limiting toxicity, maximum tolerated dose, and recommended phase II dose

A dose limiting toxicity (DLT) is defined as any of the following adverse events occurring within cycle 1 (28 days). A maximum tolerated dose (MTD) is defined as the highest dose studied for which the incidence of DLT is less than 33%. The recommended phase II dose (RP2D) is the dose with clinical efficacy without major toxicity.

- Any AE resulting in a dose delay of >7 consecutive days within the DLT period based on dose modifications in Table 9-6
- Non hematologic AE:
 - Hemorrhage requiring transfusion or procedural intervention, intracranial hemorrhage, intraocular hemorrhage of any grade
 - Grade 4 arterial hypertension
 - Any Grade ≥ 3 AE EXCEPT noted below
 - Grade ≥ 3 nausea, vomiting, constipation or diarrhea persisting for <48 hours
 - Grade ≥ 3 rash or skin hypersensitivity persisting for <7 days
 - <7 days of Grade ≥ 3 fatigue
 - <7 days of Grade ≥ 3 edema
 - <7 days of post infusion blood glucose >250 mg/dL despite optimal glucose management or <2 days of blood glucose >500 mg/dL despite optimal glucose management

- Grade 3 (or 4) isolated electrolyte abnormalities that resolve, with or without intervention, to Grade \leq 2 in less than 72 hours Hematologic AE
 - Any Grade 4 neutropenia lasting more than 7 consecutive days
 - Febrile neutropenia \geq Grade 3 (ANC $<1000/\text{mm}^3$ with a single temperature of $>38.3^\circ\text{C}$ or a sustained temperature of $\geq 38^\circ\text{C}$ for more than 1 hour

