9.5. Pharmacokinetics

Plasma concentrations of copanlisib, its metabolite M-1, and other metabolites if needed, and of ibrutinib will be measured at the following time points for pharmacokinetic (PK) assessment of patients in the phase I dose level 1 and 2 cohorts (see Table 9-4).

Table 9-4. Pharmacokinetic assessments

Cycle	Day	Planned time (h) after start of administration	Acceptable time window	Ibrutinib PK sampling	Copanlisib PK sampling	Ibrutinib dosing	Copanlisib dosing
1	15	0 (pre-dose)	- 30 min	X	X	X	X
		1 (end of Infusion) ^a	+ 5 min	X	X		
		1.5	\pm 15 min	X	X		
		2.5	\pm 30 min	X	X		
		3.5	\pm 30 min	X	X		
		4.5	\pm 30 min	X	X		
		6	\pm 30 min	X	X		

C_{max} = Maximal plasma concentration; EoI = End of infusion; PK = Pharmacokinetic(s).

a: The end of infusion sample for copanlisib and M-1 metabolite should be collected within 5 min after the end of infusion (EoI) of copanlisib for adequate characterization of C_{max} .

Samples should be collected at the planned time points as per Table 9-4, ideally within the allotted time windows. If samples are drawn outside the time window, it will not be considered a protocol deviation but the actual time of the blood draw should be noted. If clinically indicated, PK samples may be skipped without being considered a protocol deviation. For all samples, it is of importance that the actual date and time of blood sampling are documented in the eCRF because PK calculations will be based on the actual sampling times relative to dosing times.

Details about the collection, processing, storage and shipment of samples are provided separately in the Laboratory Manual.

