E: Post Infusion Blood Pressure Evaluation: Blood pressure (5-10min, +/- 10 min) prior to copanlisib must be <150/90mmHg for two consecutive measurements. If blood pressure prior to infusion is ≥150/90 mmHg, medical intervention or dose delay should be considered. Blood pressure post infusion should be measured at 30 min (mid-infusion), 60 min (end of infusion), 1 hour and 2 hour post infusion (+/- 10 min).
F: Radiographic assessment via PET and CT chest/abdomen/pelvis and neck CT if clinically indicated (MRI will be used for those who are unable to undergo CT scans).
G: Pretreatment archived biopsy material (10-15 x 10 microns) or an optional pretreatment core biopsy (2-3 cores). Post treatment optional core biopsy (2-3 cores).
H: Maximum 36 cycles, not exceeding 36 months of treatment
J: Exact schedule for PK testing is in Table 9-4.
K: Not required to collect if patient has begun new anti-cancer therapy within 30 days after last dose of either study drug on protocol.

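### Copanlisib AUC(0-24) is a main PK parameter, but sampling stops at 6 h, 18 of the 24 h are unsampled, and no extrapolation rule is given

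*Combined protocol and SAP*

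**What the plan says.** The parameter table in Section 14.4 gives the main copanlisib parameters as "Cycle 1 Day 15 Cmax, AUC(0–24". On method, the section states: "A non-compartmental analysis (NCA) will be performed in this study and pharmacokinetic parameters will be calculated using WinNonlin, in the latest version". It describes no extrapolation rule, no acceptance rule for a terminal slope and no population model.

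Section 9.5 sets the sampling: "Samples should be collected at the planned time points as per Table 9-4". The time axis of that table is "Planned time (h) after start of administration", and its rows are pre-dose, 1 (end of infusion), 1.5, 2.5, 3.5, 4.5 and 6 h on Cycle 1 Day 15, for both drugs. The 6 h draw has a window of ±30 min. Draws outside the window are not deviations, samples may be skipped if clinically indicated, and calculations use actual times.

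Table 10-1 marks PK on Cycle 1 Day 15 only, has no Day 16 visit, and refers back in a footnote: "Exact schedule for PK testing is in Table 9-4".

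On dosing, Section 9.1 says of copanlisib "Dosing is weekly for the first 3 weeks of a 28-day cycle (on Days 1, 8, and 15", and of the infusion: "Study drug is administered in a normal saline solution, intravenously, over 1 h (or per MSK protocol". For ibrutinib it says: "Ibrutinib will be administered once daily continuously until disease progression".

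Section 2.3 places the pharmacokinetics of both drugs among the exploratory assessments, for phase I dose escalation only.

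**The concern.** A main parameter is named that the schedule does not measure. The 6-24 h part of the copanlisib AUC has to come from a slope fitted to samples taken within 6 h of the start of a 1 h infusion, when distribution may still be under way. If it is, the fitted slope is too steep and the AUC comes out too low. With at most 18 patients in phase I, a low and variable AUC could be misread as low exposure, and nothing in the plan would tell a reader how much of it was extrapolated.

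The other analytes are better served. Ibrutinib is taken daily, so its pre-dose value could stand in for a 24 h value if steady state is assumed. AUC(0-tlast), which a 6 h schedule supports, is listed for ibrutinib and for the copanlisib metabolite M-1, but not for copanlisib itself.

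**Working it through.** The documents give no AUC fraction or copanlisib half-life, so there is no stated figure to reproduce. All half-lives below are assumptions.

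**Inputs from the documents.** Sampling at 0, 1, 1.5, 2.5, 3.5, 4.5 and 6 h (Table 9-4); infusion of 1 h, copanlisib on Days 1, 8 and 15 (Section 9.1); target interval 0-24 h (Section 14.4).

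**Step 1: time unsampled.** (24 − 6)/24 = 18/24 = 75%. This needs no assumption.

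**Step 2: the pre-dose sample.** Day 15 − Day 8 = 7 days = 168 h after the previous dose. It is not a 24 h concentration.

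**Step 3: share of the area after 6 h, one compartment.** With k = ln 2 / half-life and a 1 h constant-rate infusion, concentration after the infusion is proportional to (1 − e^(−k))·e^(−k(t−1))/k. Integrating gives

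share = (1 − e^(−k))·(e^(−5k) − e^(−23k)) / [k − (1 − e^(−k))·e^(−23k)].

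Example, half-life 6 h: k = 0.1155; 0.0536 / 0.1079 = 0.497.

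| Assumed half-life (h) | Share of AUC(0-24) after 6 h |
|---|---|
| 2 | 15% |
| 3 | 28% |
| 6 | 50% |
| 12 | 63% |
| 24 | 70% |
| 60 | 74% |

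The share reaches 20% at a half-life of about 2.4 h and 50% at about 6.1 h. Carry-over from the Day 1 and Day 8 doses changes it by less than one percentage point.

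**Step 4: share with an early distribution phase.** With a fast half-life of 0.5-1 h and a slow-phase coefficient share of 5-80%, the share after 6 h is about 22-63% for a terminal half-life of 12 h and about 31-72% for 36 h. A strong distribution phase can therefore keep it below half even when the terminal half-life is long.

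**Step 5: error of slope-based extrapolation.** Assumed ranges: distribution half-life 1-1.5 h, terminal half-life 12-39 h, slow-phase coefficient share f = 5-80%. The concentration is (1 − f) times the fast-phase curve plus f times the slow-phase curve, each of the form in Step 3. A log-linear slope λ is fitted to the 3.5, 4.5 and 6 h values, and

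estimate = AUC(0-6) + C(6)·(1 − e^(−18λ))/λ.

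- Near the low end (1.25 h, 39 h, f = 20%): λ = 0.176, C(6) = 0.220, extrapolated part 1.20 against a true 2.86. Ratio (2.42 + 1.20)/5.28 = 0.69.
- Near the high end (1 h, 12 h, f = 80%): λ = 0.0693, C(6) = 0.587, extrapolated part 6.04 against a true 6.52. Ratio (4.05 + 6.04)/10.57 = 0.95.

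Over the whole grid the estimate is about 69-95% of the true AUC(0-24), below it in every case. The 3.5-6 h fitting window is my choice, because the plan names none.

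**The case against.** **A reader might infer that most of the copanlisib AUC would be extrapolated.** The documents do not support that. Only the time share, 75%, is certain. By area, the share depends on a half-life the documents do not give.

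**The pre-dose sample is not useless.** If quantifiable, it is a late concentration, and the 6-24 h part could be interpolated log-linearly between the 6 h value and that trough. Under the ranges of Step 5, with a slow-phase share of 10-80%, this gives 1.00-1.22 of the true AUC(0-24), and stays within 5% when the slow-phase share is at least half. That is a fair point, but the plan does not prescribe it, it errs upward where the slope method errs downward, and with a short half-life the trough may not be quantifiable. It shows that the result depends on a method still to be chosen.

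**The consequence is limited.** PK is exploratory, and escalation and the MTD rest on dose-limiting toxicities. A reader might also infer that a drug-interaction conclusion is at risk, but Section 14.4 plans no interaction analysis, comparator PK or PK hypothesis test. Half-life, clearance and volume stand in the ibrutinib column, qualified as dependent on feasibility, so they are no part of this point. All of this stands and sets the weight of the finding. It does not remove the mismatch between Section 14.4 and Table 9-4.

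**Conclusion.** The point holds as a mismatch between the named parameter and the sampling schedule. For copanlisib, 18 of the 24 h are unsampled, the pre-dose value cannot fill the gap directly, and no extrapolation rule exists. The share of AUC(0-24) after 6 h runs from about 15% to 74% for assumed one-compartment half-lives of 2 to 60 h. Under the assumed two-phase kinetics the slope method underestimates by about 5-31% (100 − 95 and 100 − 69). These sizes rest on assumed half-lives and, for the underestimate, on the 3.5-6 h fitting window. Cmax, the MTD and the primary endpoints are not affected. The change is worth making because it is cheap and replaces an uncontrolled extrapolation with a measured quantity.

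**What to change.** In the Section 14.4 table, make AUC(0-6) on Cycle 1 Day 15, calculated from actual sampling times, the main copanlisib exposure parameter next to Cmax. Use the fixed 0-6 h interval rather than AUC(0-tlast): the last draw has a ±30 min window and may be late or skipped, so tlast would differ between patients. State how AUC(0-6) is obtained when the last actual sample is before or after 6 h, and when it is missing.

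Drop copanlisib AUC(0-24), or move it to the additional parameters and report the percent extrapolated for each patient, with the extrapolation method stated in advance. If AUC(0-24) is to stay a main parameter, the plan would need a sample near 24 h, which means a Day 16 draw that neither Table 9-4 nor Table 10-1 contains.

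Cost: the recommended change is wording only, with no extra visit or sample. The downside is that a partial AUC is less comparable with full AUCs from other studies.

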15.1 RESEARCH PARTICIPANT REGISTRATION AND RANDOMIZATION PROCEDURES

15.2 Research Participant Registration

Confirm eligibility as defined in the section entitled Inclusion/Exclusion Criteria. Obtain informed consent, by following procedures defined in section entitled Informed Consent Procedures. During the registration process registering individuals will be required to complete a protocol specific Eligibility Checklist. The individual signing the Eligibility Checklist is confirming whether or not the participant is eligible to enroll in the study. Study staff are responsible for ensuring that all institutional requirements necessary to enroll a participant to the study have been completed. See related Clinical Research Policy and Procedure #401 (Protocol Participant Registration).

15.3 Randomization

NA

16.1 DATA MANAGEMENT ISSUES

A Research Study Assistant (RSA) will be assigned to the study. The responsibilities of the RSA include project compliance, data collection, abstraction and entry, data reporting, regulatory

monitoring, problem resolution and prioritization, and coordinate the activities of the protocol study team.

The data collected for this study will be entered into a secure database (Medidata) at Memorial Sloan Kettering Cancer Center. Source documentation will be available to support the computerized patient record.

16.2 Quality Assurance

Registration reports will be generated on an ongoing basis to monitor patient accruals and completeness of registration data. Routine data quality reports will be generated to assess missing data and inconsistencies. Accrual rates and extent and accuracy of evaluations and follow-up will be monitored periodically throughout the study period and potential problems will be brought to the attention of the study team for discussion and action.

Random-sample data quality and protocol compliance audits will be conducted by the study team, at a minimum of two times per year, more frequently if indicated.

16.3 Data and Safety Monitoring

The Data and Safety Monitoring (DSM) Plans at Memorial Sloan-Kettering Cancer Center were approved by the National Cancer Institute in September 2001. The plans address the new policies set forth by the NCI in the document entitled "Policy of the National Cancer Institute for Data and Safety Monitoring of Clinical Trials" which can be found at:

<http://cancertrials.nci.nih.gov/researchers/dsm/index.html>.

The DSM Plans at MSKCC were established and are monitored by the Office of Clinical Research. The MSKCC Data and Safety Monitoring Plans can be found on the MSKCC Intranet at:

<https://one.mskcc.org/sites/pub/clinresearch/Documents/MSKCC%20Data%20and%20Safety%20Monitoring%20Plans.pdf>

There are several different mechanisms by which clinical trials are monitored for data, safety and quality. There are institutional processes in place for quality assurance (e.g., protocol monitoring, compliance and data verification audits, therapeutic response, and staff education on clinical research QA) and departmental procedures for quality control, plus there are two institutional committees that are responsible for monitoring the activities of our clinical trials programs. The committees: Data and Safety Monitoring Committee (DSMC) for Phase I and II clinical trials, and the Data and Safety Monitoring Board (DSMB) for Phase III clinical trials, report to the Center's Research Council and Institutional Review Board.

During the protocol development and review process, each protocol will be assessed for its level of risk and degree of monitoring required. Every type of protocol (e.g., NIH sponsored, in-house sponsored, industrial sponsored, NCI cooperative group, etc.) Will be addressed and the monitoring procedures will be established at the time of protocol activation.

17.1 PROTECTION OF HUMAN SUBJECTS

Potential risks to human subjects include drug related toxicity; pain and discomfort associated with therapy; treatment side effects; phlebotomy; and possible psychologic discomfort from the stresses associated with obtaining imaging studies (e.g., CT scan, PET scan).

The side effects and potential toxicities of all agents are listed in sections 5.0 and 11.0. All efforts will be made to avoid any complication by completely reviewing patients' symptoms, providing appropriate management, and monitoring blood tests.

If an adverse medical event occurs, the patient will first contact the primary oncologist or the principal investigator. At nights and weekends, there is an oncology physician on call at all times. Patients may either call or come directly to the Urgent Care Center at Memorial Hospital (or to their local emergency room) to be seen.

Costs to the patient (third party insurer) will include the cost of blood tests and diagnostic studies, office visits, and those admissions which may be required as a consequence of treatment-related complications.

All serious adverse events incurred while a patient is on study will be reported to the IRB at Memorial Hospital, and Bayer. All serious adverse experiences and relevant laboratory findings will be reported to the principal investigator immediately. An adverse experience is considered serious if death occurs, the condition is life threatening, hospitalization is required, or there is permanent disability or incapacity. All information regarding serious adverse experiences must be recorded on the form provided. Patients suffering serious adverse reactions must be carefully followed and all follow-up information also recorded.

All life threatening and lethal known, unknown, or suspected reactions (toxicities) must be reported to the principal investigator. An SAE report will be submitted to Bayer within 24 hours of the principal investigator's knowledge of the event, and the IRB within 5 days. Any death, regardless of cause, must be reported to the principal investigator by telephone or fax and in writing. It is the treating physician's responsibility to investigate and report the date and cause of death of any patient entered on this trial.

